2. Known to have medication treatment adherence problems as identified by the Treatment Routines Questionnaire (TRQ, 20% or more missed medications in past week or past month)
3. Screening BPRS score of ≥ 36
4. Ability to be rated on psychiatric rating scales.
5. Willingness to take LAI
6. Currently in treatment or scheduled to receive treatment at a Community Mental Health Clinic (CMHC) or other clinical setting able to provide mental health care during and after study participation
7. Able to provide written, informed consent to study participation.

Exclusion Criteria:

1. Individuals on LAI immediately prior to study enrollment.
2. Individuals with known intolerance or resistance to either oral aripiprazole or LAI formulation of aripiprazole
3. Prior or current treatment with clozapine
4. Medical condition or illness, which in the opinion of the research psychiatrist, would interfere with the patient's ability to participate in the trial
5. Physical dependence on substances (alcohol or illicit drugs) likely to lead to withdrawal reaction during the course of the study in the clinical opinion of the treated research psychiatrist
6. Immediate risk of harm to self or others
7. Female who is currently pregnant or breastfeeding

Study Medication: Medication dosing will follow recommendations in the Maintena package insert. For patients who have never received aripiprazole, there will be a brief oral tolerance testing (OTT) of up to 14 days. Individuals who tolerate OTT will then receive 400 mg of Maintena administered IM in the gluteal or deltoid location, and oral Abilify will continue for an additional 14 days, after which oral medication will be discontinued. After the initial IM injection, individuals will continue to receive injections of Maintena every month for a total of 6 months. The standard dosage of 400 mg IM will be administered in this maintenance treatment phase although clinicians may administer a lower dosage of 300 mg IM depending on clinical response.

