Safety evaluations will include baseline and Week 24/End-of-study basic laboratory evaluations (comprehensive metabolic panel, lipid profile, CBC with differential) and pregnancy testing for women. EKG will be conducted at baseline, week 4 and Week 24/End-of-study. Patient vital signs and weight will be collected at each study visit (baseline/V1, V2, V3, V4, V5, V6, V7, V8). Standardized measures of involuntary movements/ extrapyramidal symptoms will be assessed with the Simpson Angus Scale (SAS), the Barnes Akathisia Scale (BAS), the Abnormal Involuntary Movement Scale (AIMS) and the Extrapyramidal Symptoms Scale-Abbreviated version (ESRS-A). Finally, reported side effects will also be evaluated at each study visit using a form derived from the previous CAE-L studies.

Table 2: Measures and Study Schedule of Events

Visit	Screen	BL/ V1	V2	V3	V4	V5	V6	V7
Timing [†]	-14 d to -1d	0 W	4W	8W	12W	16W	20W	24W
Informed consent	X							
Inclusion/Exclusion	X							
Adherence Behavior: TRQ LAI Injection Frequency*	X	X	X	X	X	X	X	X
Non-psychotropic drug TRQ	X				X			X
MINI	X							
CAE module allocation and assessment of Adherence barriers	X							X
Physician Exam and interview	X							X
Demographics, medical burden	X							
Laboratory testing	X				X			X
EKG	X		X					X
Adherence Attitudes: DAI, AMSQ		X			X			X
Symptoms: BPRS, YMRS, MADRS, CGI	X†	X			X			X
Functioning: SOFAS, GAF		X						X
Health resource use		X						X
Alcohol/Substance Use: AUDIT, DAST-10		X			X			X
Trails A & B, Animal Fluency	X							X
Weight and vitals		X	X	X	X	X	X	X
Reported Side Effects		X	X	X	X	X	X	X
Extrapyramidal symptoms: AIMS**, SAS, BAS, ESRS-A	X	X	X	X	X	X	X	X
Patient Satisfaction					X			X
Research Clinician assessment		X	X	X	X	X	X	X
CAE sessions		X	X	X	X	X	X	X
Oral aripiprazole Dispensing***	X	X						
LAI Injection		X	X	X	X	X	X	X

[†]Timing of visits is approximate.

* LAI Injection frequency will be calculated at weeks 12 & 24.

** AIMS will only be administered at BL and W24/Term

*** Dispensing of oral medication is patient specific and may include a 14-day oral tolerability test prior to first LAI injection, or dispensing of anti-side effect medications.

† BRPS will be the only symptom evaluated at screen

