Laboratory testing includes: Comprehensive metabolic panel, CBC with differential, Thyroid function. Pre-menopausal females will require serum pregnancy testing. Women of childbearing potential must be using medically accepted methods of birth control. Week 12 lab testing will only include serum pregnancy testing for pre-menopausal females. Pregnancy testing may also be done at any time point if a woman feels she may be pregnant.

Serious Adverse Event Reporting

1. Serious adverse events (SAEs) and other safety information will be collected and reported to the relevant government authority in accordance with the current Code of Federal Regulations
2. Safety Information is defined as, any information from any source containing information such as:
 - Adverse event or suspicion thereof
 - Lack of efficacy
 - Overdose/incorrect dosage (accidental or intentional)
 - Abuse/misuse (e.g., patients sharing medication) even without resulting adverse reaction
 - Accidental exposure (e.g., child takes parent's medication)
 - Medication error
 - Withdrawal reactions
 - Disease progression/exacerbation of existing disease
 - Drug-drug/Drug-food interaction
 - Reports of unexpected benefit
 - Exposure to drug during pregnancy, where the embryo or fetus may have been exposed to medicinal products (either through maternal exposure or transmission of a medicinal product via semen following paternal exposure).
 - Exposure to drug during lactation (including uneventful)
 - Suspected counterfeit product
 - Suspected transfer of infectious disease/agent by the medicinal product concerned.
 - Product complaint report (any deficiencies related to the identity, quality, labeling, durability, reliability, efficacy, performance of a medicinal product, suspected counterfeit product)
 - Pediatric use (if not an approved use)
 - Occupational exposure
 - Off-label use (if not part of the study design)
3. SAEs and safety information will be collected from first use of an Otsuka product until 28 days after discontinuation.

Data Management & Analyses: Study data will be collected and managed using REDCap(Harris 2009), a secure, web-based application designed to support data capture for research studies.

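### Table 2 puts a seventh depot injection at its last dated visit, so the promised 28-day safety collection has no dated contact unless six injections are intended (minor, cheap to fix)

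*Combined protocol and SAP*

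**What the plan says.** - **Safety window (Serious Adverse Event Reporting).** "SAEs and safety information will be collected from first use of an Otsuka product until 28 days after discontinuation". The section does not define discontinuation and names no visit or call for the period. It defines safety information broadly, as "any information from any source containing information such as" a list of event types.
- **Injection schedule (Table 2).** The row reads "LAI Injection X X X X X X X", with the Screen cell blank and one mark at each of V1 (week 0) to V7 (week 24). V7 is the last column. A footnote adds: "Timing of visits is approximate".
- **Injection count in the text.** Study Medication says that, after the first dose, "individuals will continue to receive injections of Maintena every month for a total of 6 months", which can be read as six doses in all or as one plus six. Sample Size and Power supposes six over six months.
- **Visit list (Safety Evaluations).** "Patient vital signs and weight will be collected at each study visit (baseline/V1, V2, V3, V4, V5, V6, V7, V8". The same paragraph has reported side effects assessed at every study visit. V8 appears nowhere else.
- **Early stoppers.** A Table 2 footnote says "AIMS will only be administered at BL and W24/Term", so a termination assessment is foreseen, but nothing ties it to the date of the last injection.
- **Aftercare (Inclusion Criteria).** Patients must be in, or scheduled for, treatment at a community clinic or "other clinical setting able to provide mental health care during and after study participation".

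**The concern.** A site works from the schedule of events. Followed literally, Table 2 has the site give a depot dose, which the Background says covers 30 days, on the same day as the closing laboratory tests, EKG, movement scales and side-effect form. None of those can show a later effect of that dose. Events in the following 28 days would reach the study only if the patient or an outside clinician volunteered them. Some of what the plan counts as safety information, such as withdrawal reactions or exposure in pregnancy, can arise in that period.

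The same ambiguity touches a primary outcome, because the number of prescribed injections is the denominator of injection frequency.

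**Working it through.** **Inputs.** Visit weeks and injection marks come from Table 2. The 28-day window comes from Serious Adverse Event Reporting. Six injections, SD of 20% of injections, the 80% threshold, 30 patients and 20% attrition come from Sample Size and Power. Day = week × 7. The window is taken to start at the last injection, which is an assumption because discontinuation is undefined.

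**The plan's own injection criterion.** With n = 30 × 0.80 = 24, threshold 0.80 × 6 = 4.8 and SD 0.20 × 6 = 1.2:

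4.8 + 1.96 × 1.2/√24 = 4.8 + 0.48 = 5.28, and 5.28/6 = 88.0%. This matches the plan.

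With seven injections, the threshold is 5.6 and the SD 1.4:

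5.6 + 1.96 × 1.4/√24 = 5.6 + 0.56 = 6.16, and 6.16/7 = 88.0%. The criterion, as a percentage, does not depend on the count.

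**Coverage of the window.**

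| Reading | Last dose | Window ends | Last dated visit | Days of window after it |
|---|---|---|---|---|
| Seven injections (Table 2) | week 24, day 168 | 168 + 28 = day 196 (week 28) | V7, day 168 | 196 − 168 = 28 |
| Six injections (Sample Size and Power) | week 20, day 140 | 140 + 28 = day 168 | V7, day 168 | 0 |

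Continuing the 4-week spacing, V8 would fall at week 28 (day 196) and close the gap in the first row. That date is inferred; the plan gives none.

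**Sensitivity under six injections.** The Adherence paragraph counts a dose as adherent if it is within 7 days of schedule. If the V6 dose is given on day 147 and V7 stays on day 168, V7 is 21 days after the dose and 28 − 21 = 7 days are uncovered. If V7 moves with the dose, nothing is uncovered.

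**Patients concerned.** Expected completers: 30 × 0.80 = 24. Expected early stoppers: 30 × 0.20 = 6.

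**The case against.** The strongest objection is that the completer gap hangs on one table cell. The power section supposes six injections, Study Medication can be read the same way, and on that reading V7 lands on the last day of the window. This stands, so the gap has to be stated conditionally. It does not remove the point, because Table 2 is what sites follow and the conflict between six and seven still has to be settled.

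Second, V8 is more than a stray label. Since Safety Evaluations lists it among the study visits and has side effects assessed at all of them, V8 would carry vitals, weight and the side-effect form. That also stands. It may be an intended follow-up visit or a numbering slip (screening plus seven visits makes eight). Without a date or a Table 2 column, it does not yet deliver a contact.

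Third, the commitment already exists, reports from any origin are accepted, and patients have an aftercare setting. These give partial cover, but none is a planned study contact. Consent pages are not in the available text, so instructions there about contact after the study cannot be ruled out.

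A reader might infer three stronger things that the documents do not support:

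- **That six injections still leave 7 of the 28 days uncovered.** This holds V7 fixed when visit timing is approximate.
- **That all six expected early stoppers go unobserved.** A patient who declines a dose at a 4-weekly visit is seen about 28 days after the previous one, and some who leave will be unreachable by any means.
- **That patients face a demonstrated safety risk.** The documents give no event rate, and a V7 dose would repeat a drug already given at six visits with side effects assessed.

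**Conclusion.** The point holds as a minor one. The plan is inconsistent on the number of injections (six or seven) and on the last visit (V7 or V8), and it promises 28 days of safety collection without a dated contact to deliver it. If Table 2 is followed, the whole window, days 169 to 196, has no dated contact for about 24 completers (at most 30 patients). If six injections are intended, completers have no nominal gap. Under either count, early stoppers have no contact timed to their last dose, though some will be seen near 28 days anyway.

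This rests on nominal 4-week visits, on the window starting at the last injection, and on the plan's 20% attrition. No efficacy conclusion depends on it, and the 88% criterion is unaffected.

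**What to change.** 1. State one injection count in Table 2, Study Medication and Sample Size and Power, and use it as the denominator of injection frequency.
2. If seven: date V8 at about week 28 and add it to Table 2, as a visit or a telephone safety contact using the existing side-effect form.
3. If six: remove the V7 injection mark, delete V8 from Safety Evaluations, and say whether the V7 adherence session stays, since those sessions are placed on the injection day.
4. Under either count, state that the 28 days run from at least the last injection. This sets a minimum and leaves room for a later definition of discontinuation. Make one telephone contact at or after 28 days for any reachable patient, early stoppers included, who has no study visit that late.

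**Cost.** At most 30 short calls by existing staff with an existing form, about one more month of contact per patient, and a few text edits. With six injections, calls are needed only for early stoppers (about 6 expected, fewer if some are unreachable or were seen late enough) and for any completer whose V7 falls less than 28 days after the last dose.

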Customized Adherence Enhancement (CAE) is a brief behavioral intervention that improves adherence approximately 30% more than an educational control in adults with BD. The CAE program is a brief, practical intervention consisting of a series of up to four psychosocial treatment modules based upon an adult's unique adherence barriers: 1) Psychoeducation on BD Medications; 2) Communication with Providers; 3) Strategies to Enhance Medication Routines; and 4) Targeting Substance Use Problems with Modified Motivational Enhancement Therapy. These CAE modules are derived from existing evidence-based approaches for patients with BD (Bauer 2004, Bauer 2006a, Bauer 2006b, Frank 2005, Sajatovic 2005, Ziedonis 2005). Each CAE module can be combined with other CAE modules. The material can be delivered in approximately 6 in-person sessions.

These investigators conducted 2 pilot trials of CAE that were nearly identical in design. The first trial was an NIMH-funded 6-month pilot evaluating the feasibility/acceptability and preliminary efficacy of CAE in 43 poorly adherent BD adults (Sajatovic 2012a) and the second trial was an industry-funded 3-month trial in 43 poorly adherent BD adults (Sajatovic 2012b). In both trials, the primary outcome was adherence evaluated with the Tablet Routines Questionnaire (TRQ; Peet 1991, Scott 2002). Pooled results indicated mean baseline non-adherence (proportion of missed medication) was 40.2% (SD 31.6%) within the past week and 42.8% (SD 28.1%) missed medication within the past month. At 3 months, mean missed medication decreased to 18.5% (SD 31.9) for the past week, and 15.8% (SD 26.1%) for the past month. At 6-month follow-up, mean missed tablets was 25.2% (SD 36.2%) for the past week and 21.3% (SD 29.1%) for the past month.

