An important limitation of the CAE-L pilots is that they excluded individuals with BD. The pilot studies combined LAI + CAE data suggested that patients with schizoaffective disorder (N=44) did just as well as those with schizophrenia (N=16) with respect to adherence, symptom and functional outcomes (Levin et al., 2017). Combining Maintena with a practical method of adherence support has potential to enhance uptake and optimize enduring adherence to medication in patients with BD.

Project Design:

Overview: 6-month, prospective, trial testing the effects of Maintena augmented with CAE in 30 poorly adherence patients with BD. After a 2-month study start-up period, patients will be enrolled over a 16 month enrollment period (months 2-18). The targeted enrollment of approximately 2 participants/month is reasonable given previous recruitment with the CAE + LAI pilots. Primary outcomes will be change from baseline in adherence as identified by the Tablet Routines Questionnaire (TRQ) and injection frequency at the 6-month time-point. We will also evaluate changes in secondary outcomes, including BD symptoms (BPRS), depressive and global psychopathology symptoms, functional status, and adherence attitudes. Additional exploratory assessments will include health resource use, adherence barriers, substance use and neurocognition. Outcome measures will be assessed at Screening, Baseline, and Weeks 4- 24 as noted in Table 2/Study Schedule of Events. Because the study design will be nearly identical to the 2 previously conducted CAE + LAI pilots, it will be possible to compare primary and secondary outcomes of this study of individuals with BD to individuals with schizophrenia/schizoaffective disorder. The study will be operationalized in 4 specific Aims:

Aim 1: Test whether combined Maintena + CAE (Maintena +) is associated with improved treatment adherence

[figure not shown]
Hypothesis 1: At 6-month follow-up, poorly adherent BD patients receiving Maintena + will have significant improvement in medication adherence as measured by the TRQ.

Hypothesis 2: At 6-month follow-up we also expect that mean LAI adherence as measured by injection frequency will meet or exceed 80%. The 80% threshold is widely viewed in the treatment adherence literature as an “acceptable” degree of adherence.

Aim 2: Test whether Maintena + is associated with reduction in BD symptoms, improved functioning and better treatment attitudes

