Sample Size and Power: We propose to enroll 30 individuals with BD who receive Maintena +. Based on our prior studies (Sajatovic 2012a, Sajatovic 2012b), we conservatively assume 20% of participants will discontinue study participation during the 24 week study period and that the effect size of CAE-L will be similar to that of CAE-L in prior studies (effect size $d=.60$). Type I error level of 0.05 will be adopted for all tests.

The primary outcomes measure will be change in adherence behavior and the mean LAI injection frequency at 6-months. Adherence rates will be calculated for TRQ in the following manner: the number of days with a missed dose will be divided by the number of days in the time period and then multiplied by 100. Adherence rates will be calculated for both the week and the month prior to assessment visit and for the study period. Given a sample size of 30 subjects with 20% attrition and two-sided Type I error of 0.05, for paired t-tests we will have power of 0.80 for effect sizes of at least 0.597. For correlations, power of 0.80 is achieved for a two-sided test of correlation being zero when the magnitude of correlation is at least 0.51. Hence, there is sufficient power to detect moderate level mean differences and correlation values. For the assessment of mean injection frequency, suppose 6 prescribed injections in 6 months, with a standard deviation of 1.2 (20% of prescribed injections). Then, if a sample mean of 5.28 or higher is observed (88%), a 95% two-sided confidence interval will not contain 4.8, the 80% threshold, This would provide evidence that the percentage of injection frequency is higher than 80%. Note that adherence levels of 80% or higher are widely considered to be "acceptable" adherence in the research literature. The mean LAI injection frequency in our previous pilot work involving LAI + CAE in homeless patients with schizophrenia exceeded 90% of prescribed injections at 6-month follow-up. We thus expect to statistically establish that the mean LAI injection frequency in this bipolar sample who are not homeless is above the 80% threshold.

Data analyses will be performed using the Statistical Analysis System (SAS) (SAS Institute, Cary, NC, 2002).. For Aim 1, change in TRQ from baseline to 24 weeks will be assessed with a paired t-test or Wilcoxon signed rank test. For mean LAI injection frequency, we will construct 95% confidence intervals. Exploratory longitudinal

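### Hypothesis 1 names no TRQ look-back window, although past-week and past-month rates are both calculated and every test is run at 0.05

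*Combined protocol and SAP*

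**What the plan says.** All references are to the combined protocol and SAP.

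- **Hypothesis 1** (Project Design, Aim 1) expects, at 6 months, "significant improvement in medication adherence as measured by the TRQ". The Overview and the Measures section also give the primary outcome as the TRQ, without a look-back period.
- **Calculation of the TRQ** (Sample Size and Power): "Adherence rates will be calculated for both the week and the month prior to assessment visit and for the study period".
- **Aim 1 test** (analysis text after the power statement): "change in TRQ from baseline to 24 weeks will be assessed with a paired t-test or Wilcoxon signed rank test". The start and end points are fixed; the window and the choice between the two tests are not.
- **Error rate** (Sample Size and Power): "Type I error level of 0.05 will be adopted for all tests".
- **Entry** (Inclusion Criterion 2) accepts 20% or more missed medication in either window, so it does not point to one of them.
- **Power** (Sample Size and Power): 30 enrolled, 20% attrition, and 0.80 power for a paired t-test at an effect size of at least 0.597. The assumed effect is .60, on the premise that "the effect size of CAE-L will be similar to that of CAE-L in prior studies". For correlations, 0.80 power is stated at a magnitude of at least 0.51.
- **Reporting** (Study reporting/deliverables) expects interim results to be used for abstracts while the study is running.

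**The concern.** The TRQ produces at least two change scores per patient, and the plan has no rule for which one decides Hypothesis 1. If past week reaches significance and past month does not, or the reverse, the text supports a claim of success as readily as a claim of failure. That gives one hypothesis two chances at 0.05, and a reader of the final report could not tell which result was meant to count.

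Timing adds to this. The study is unblinded and interim results may be reported, so a window named after those looks could not be presented as prespecified.

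A second, smaller issue is that the assumed effect of .60 is not linked to a window, a starting point or a standard deviation of change.

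**Working it through.** **1. The plan's own power figure.** Evaluable patients: 30 × (1 − 0.20) = 24. For a two-sided paired t-test at 0.05 with 23 degrees of freedom and noncentrality d√24, power is 0.7998 at d = 0.597 and 0.804 at d = .60. The smallest effect detectable with 0.80 power is 0.597. The plan's figure reproduces and holds for either window.

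**2. Error rate if either window suffices.** Suppose there is no true change in either window. Each test alone gives a false improvement with probability 0.025 and a significant result in either direction with probability 0.05. If the two tests were independent:

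- improvement on either: 1 − 0.975² = 0.049
- either direction on either: 1 − 0.95² = 0.0975

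The past week lies inside the past month, so the change scores should be positively correlated and the true figures lower. The plan reports no such correlation, so it is assumed here. Simulation of two paired t-tests with n = 24, normal change scores and 400,000 runs per row:

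| Correlation of the two change scores (assumed) | False improvement on either (nominal 2.5%) | Either direction (nominal 5%) |
|---|---|---|
| 0.5 | 4.5% | 9.1% |
| 0.7 | 4.2% | 8.4% |
| 0.9 | 3.6% | 7.2% |

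Repeat runs agree to about 0.1 percentage point. Only two windows are counted. The study-period rate has no stated baseline counterpart, so it does not give a third change-from-baseline test.

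**3. The detectable correlation.** Aim 4 correlates changes in barriers with changes in adherence, and both are observed variables. With n = 24 and a two-sided test at 0.05, simulation from a bivariate normal distribution gives power 0.751 at a true correlation of 0.51, 0.80 at 0.535 and 0.81 at 0.54. The stated 0.51 comes close under a model that treats one variable as fixed: power 0.793 at 0.51, and 0.80 at 0.513.

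**The case against.** **The harm is small.** Hypothesis 1 claims improvement, so the relevant error is 3.6-4.5%, which stays below 5%. A significant worsening cannot support the hypothesis, and overlap between the windows makes the lower end more plausible. This stands, and is why the inflation is called modest.

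**Nothing shows an intention to select.** The Background reports both windows side by side, and the plan calculates both. This also stands. A reader might infer from the expected interim abstracts that the sponsor may choose a window after seeing data, but the reporting section does not say so. The point is only that no rule prevents it.

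**A tempting stronger reading is that the study is underpowered on past week.** In Table 1, past week goes from 26.7 (SD 29.3) at baseline to 17.1 (SD 30.6) at week 25. With an assumed within-patient correlation of 0.5:

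- SD of change = √(29.3² + 30.6² − 2 × 0.5 × 29.3 × 30.6) = 29.97
- d = 9.6 / 29.97 = 0.32

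The same formula gives 0.68 for past month (32.5, SD 30.4, to 13.8, SD 23.2). The documents do not support building on that gap:

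- The correlation is not reported.
- At N = 26, d = 0.32 gives t = 0.32 × √26 ≈ 1.6, which does not fit Table 1's .001. If Table 1's p-values (.001 at N = 26, .002 at N = 25) come from paired tests, they imply effects of about 0.73 and 0.69, and the windows hardly differ. Table 1 names neither test nor contrast, so this reading is not settled either.
- The bipolar pilots do not resolve it. Their 6-month result, "mean missed tablets was 25.2% (SD 36.2%) for the past week and 21.3% (SD 29.1%) for the past month", can come only from the 6-month pilot, whereas the baseline pools both pilots. It is not a paired effect.

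**The source of .60 may be only a loose citation.** The sentence cites the two 2012 pilots, which tested CAE without a long-acting injectable in bipolar patients, but credits the effect to CAE-L. The plan notes elsewhere: "An important limitation of the CAE-L pilots is that they excluded individuals with BD". The citation may be meant for attrition alone. That makes it a matter to clarify, not a demonstrated error.

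**Conclusion.** The point holds as a gap in the definition of the primary outcome. No section names a window, requires both, or adjusts for two, so Hypothesis 1 has two routes to success at 0.05. The cost is a false-improvement rate of about 3.6-4.5% instead of 2.5%, or about 7-9% instead of 5% in either direction. These figures rest on 24 evaluable patients, normal change scores and an assumed correlation of 0.5 to 0.9 between windows. The missing window itself rests on no assumption.

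The documents do not show that the power calculation is wrong, that .60 is too high, or that past week has less power than past month. The correlation figure is a minor inaccuracy, and the analyses it serves are exploratory. The point should be fixed, but it does not threaten the design.

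**What to change.** Before any outcome data are examined, including for abstracts, add to Sample Size and Power and carry into Aim 1:

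> *The primary TRQ outcome is the change from baseline (V1) to week 24 in the past-[week or month] rate, tested once at two-sided 0.05 by [paired t-test or Wilcoxon signed rank test]. The other window and the study-period rate are supportive and cannot establish Hypothesis 1.*

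The window and the test are the sponsor's choice. Naming the test matters too, because two tests with no rule between them would leave a second open choice.

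Keep the paired-t statement. As a note beside it, give the source, window and contrast behind d = .60. Restate the detectable correlation as about 0.54, or state the model that gives 0.51.

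**Cost.** Wording only: enrolment, visits and data collection are unchanged, and 0.80 power at 0.597 is kept for the paired t-test. Splitting alpha between the windows instead would reduce power at d = .60 with 24 evaluable patients to 0.70 per window. The downsides are that one window gives up its claim to Hypothesis 1, though it should still be reported, and that the detectable correlation looks slightly less favourable.

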models of adherence will be considered as well. We may represent adherence as a binary outcome, indicating whether or not an adherence threshold has been met (e.g., 80% adherent), particularly if adherence levels are highly skewed. Exploratory logistic regression through generalized estimating equations (GEE) or generalized linear mixed models for binary outcomes will thus be considered for assessing effects of time. Time may be modeled with a slope parameter or treated as a categorical variable. Age, race, duration of illness, and/or gender will be considered as possible covariates. In addition, we will compare corresponding TRQ and SimpleMed pillbox adherence levels. Correlation between the adherence measures will be estimated and Bland-Altman plots will be generated (Altman 1983).

Aim 2 will evaluate change from baseline to 24 weeks in TRQ, psychiatric symptoms (BPRS, MADRS, YMRS, CGI) in a similar manner as in Aim 1. For Aim 3, change in the outcome variables and other secondary measures in the proposed study vs. historical controls (the previously conducted CAE + LAI pilots) will be compared through effect sizes. In Aim 4, adherence barriers will be evaluated as well. Mean change in symptom rating scales, functional level and medication attitudes will be estimated from baseline to the various follow up periods. We will explore whether reductions in adherence barriers (e.g., BD knowledge, medication routines, communication, and substance) will be associated with changes in adherence behavior. Correlations between respective changes in barriers and adherence levels will be computed. In a similar manner, we will also examine whether improvements in adherence behaviors correlate with improvements in symptoms, functioning, and medication attitudes.

Study reporting/deliverables: Reporting on study outcomes will be focused on rapidly available and impactful findings. As the study does not require blinding, it is expected that interim results can be used for new research abstract proposals that can be submitted even while the study is ongoing. It is expected that study results will be presented at a minimum of 2-3 suitable scientific venues including (but not limited to):

- American College of Neuropsychopharmacology (ACNP)
- American Psychiatric Association (APA)
- International Society for Bipolar Disorders (ISBD)

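### With 24 evaluable patients, a correlation of 0.51 between two change scores has power of about 0.75, not 0.80; the detectable value is about 0.54

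*Combined protocol and SAP*

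**What the plan says.** The combined protocol and SAP, under Sample Size and Power, sets enrolment at 30 ("We propose to enroll 30 individuals with BD who receive Maintena") and allows for dropout: "we conservatively assume 20% of participants will discontinue study participation during the 24 week study period". The error rate is common to every analysis: "Type I error level of 0.05 will be adopted for all tests".

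Two detectable effects follow. The first is introduced by "Given a sample size of 30 subjects with 20% attrition and two-sided Type I error of 0.05" and reads "for paired t-tests we will have power of 0.80 for effect sizes of at least 0.597". The next sentence, which gives no sample size, formula or software routine of its own, says that "power of 0.80 is achieved for a two-sided test of correlation being zero when the magnitude of correlation is at least 0.51". The paragraph then concludes that "there is sufficient power to detect moderate level mean differences and correlation values".

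The use of these correlations is described later in the analysis text, for Aim 4: "Correlations between respective changes in barriers and adherence levels will be computed". The same approach is planned for adherence change against changes in symptoms, functioning and medication attitudes. The description of Aim 4 under Project Design calls the analysis of barrier change against adherence change exploratory.

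**The concern.** The two power figures stand side by side and appear to share one sample size. The paired-t figure reproduces at 24 patients by the usual calculation. The correlation figure does not reproduce at 24 by the calculation most readers would use, namely the Pearson test with both variables random, or its Fisher z approximation. It comes out too favourable.

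This is the only power statement for the correlations. If it is optimistic, the chance of missing a true correlation of 0.51 is about 25% instead of the implied 20%, and a null correlation could be read with slightly more confidence than the design supports.

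**Working it through.** **Inputs.** From Sample Size and Power: 30 enrolled, 20% attrition, two-sided alpha 0.05, target power 0.80, stated detectable r of 0.51, stated paired-t effect of 0.597. Evaluable n = 30 × 0.8 = 24; the plan does not print 24. From the Aim 4 analysis text: both correlated variables are observed changes.

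**Step 1. Which n was used? Reproduce the paired-t figure.** Power = P(T > t₀.₉₇₅,₂₃), with T noncentral t on 23 df and noncentrality d√n.
- At d = 0.597: 0.597 × √24 = 2.925, critical value 2.069, power 0.7998.
- Solving for power 0.80 gives d = 0.5972 at n = 24, against 0.529 at n = 30.

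The 0.597 matches, so the paragraph works with 24.

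**Step 2. Reproduce the stated 0.51.** Treat one variable as a fixed regressor: noncentral t, df = n − 2 = 22, noncentrality √n · r / √(1 − r²).
- At r = 0.51: √24 × 0.51 / √(1 − 0.2601) = 2.905, critical value 2.074, power 0.793.
- Solving for power 0.80 gives r = 0.5135, which rounds to 0.51.

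Of the two-sided methods tried, this is the only one that returns 0.51 at n = 24. A one-sided test does not explain the figure: it gives power of 0.82 to 0.88 at r = 0.51.

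**Step 3. The planned use, with both variables random.** Under bivariate normality the noncentrality is itself random: √V · r / √(1 − r²), with V chi-square on n − 1 = 23 df. Power is the noncentral-t power averaged over V. The fixed-regressor model sets V = 24, which is above its mean of 23 and ignores its spread. At r = 0.51 and n = 24:

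| Method | Power at r = 0.51 | r for power 0.80 |
|---|---|---|
| Fixed regressor, V = 24 | 0.793 | 0.5135 |
| Same, V = 23 | 0.776 | 0.522 |
| Exact bivariate normal | 0.750 | 0.536 |
| Fisher z with bias term | 0.748 | 0.537 |
| Plain Fisher z | 0.732 | 0.545 |

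A simulation of 400,000 bivariate-normal samples, with critical |r| of 0.404, gave 0.7505, in agreement with the exact value.

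The Fisher z rows can be checked by hand:
- Plain: atanh(0.51) = 0.5627; 0.5627 × √21 = 2.579; 2.579 − 1.960 = 0.619; Φ(0.619) = 0.732.
- Bias term: 0.51 / (2 × 23) = 0.0111; (0.5627 + 0.0111) × √21 = 2.629; less 1.960 is 0.669; Φ = 0.748.
- Detectable r, plain: tanh((1.960 + 0.842) / √21) = 0.545.

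**Step 4. Dependence on n.** Exact power at r = 0.51 is 0.731 at n = 23, 0.750 at 24, 0.769 at 25, 0.786 at 26, 0.803 at 27 and 0.845 at 30. It first reaches 0.80 with 27 complete pairs.

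**The case against.** The strongest reply is that the plan's figure does reproduce. A recognised noncentral-t calculation at n = 24 gives 0.5135, so both printed detectable effects are consistent with one sample size, and the plan names no method that would contradict this. That stands, and it rules out a stronger reading a reader might reach: that 0.51 is an arithmetic error, or was computed for a different number of patients. Another origin cannot be wholly excluded, since one Fisher z variant gives 0.510 at n = 27, but the agreement of both figures at 24 makes the fixed-regressor route the natural explanation. What the reply does not rescue is the fit of that model to two measured change scores.

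A second reply is that the gap is small: about 0.026 in r (0.536 against 0.51) and about 5 points of power. One evaluable patient more or fewer moves exact power by about 2 points, and the 20% attrition is itself an assumption. This too stands, and it limits the weight of the point.

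A reader might also infer that the sentence about moderate correlations is false, or that Aim 4 is undermined. The documents support neither. They set no benchmark for a moderate correlation, so a move from 0.51 to 0.54 does not by itself make the word wrong. Aim 4 is presented as exploratory, with no success criterion tied to 0.51.

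**Conclusion.** The point holds as a minor correction. For the correlations the plan intends, power at r = 0.51 with 24 evaluable patients is about 0.75 (0.73 by plain Fisher z), and power of 0.80 needs r of about 0.54. The printed value reflects a fixed-regressor model that is optimistic when both variables are random.

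This rests on 24 complete pairs, two-sided alpha 0.05 and approximate bivariate normality of the change scores. Missing barrier or outcome scores would lower power further.

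The primary analyses are untouched: the test of TRQ change keeps its 0.597, and the injection-frequency interval does not use the correlation figure. The sample size of 30 does not depend on it either.

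**What to change.** Under Sample Size and Power, replace 0.51 with about 0.54 for 24 evaluable patients, or keep 0.51 and state its power as about 0.75. In the same sentence, give n = 24 and name the method (two-sided Pearson test, bivariate-normal model). Let the concluding sentence on sufficient power refer to the corrected figure; the word moderate need not change.

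The cost is one figure and a short clause. The stated detectable correlation becomes slightly less favourable, and nothing in the design, enrolment or primary analysis changes.
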